7.4.2. Criteria for Conditional Withholding of Mavacamten Due to Potential Hepatotoxicity

For participants who do not meet the criteria for permanent withholding of study medication outlined above, mavacamten should be withheld if ANY of the following criteria are met, and the participant should be evaluated for DILI:

- Elevation of either AST or ALT, regardless of baseline AST or ALT value, if:
 - $> 8 \times \text{ULN}$ at any time
 - $> 5 \times \text{ULN}$ and $< 8 \times \text{ULN}$ for ≥ 2 weeks
 - $> 5 \times \text{ULN}$ and $< 8 \times \text{ULN}$ and unable to adhere to enhanced monitoring schedule
- OR: clinical signs or symptoms that are, in the opinion of the Investigator, consistent with hepatitis (such as right upper quadrant pain/tenderness, fever, nausea, vomiting, jaundice, rash, or eosinophilia $> 5\%$). If such signs or symptoms are coupled with ALT or AST elevations $> 3 \times \text{ULN}$, study medication should be withheld
- OR: TBL $> 3 \times \text{ULN}$ at any time
- OR: ALP $> 8 \times \text{ULN}$ at any time

Mavacamten should be withheld pending an investigation into alternative causes of DILI. If study medication is withheld, the participant should be followed according to recommendations in [Appendix 3](#) for possible DILI. Rechallenge may be considered if an alternative cause, such as acute hepatitis B infection, is discovered and the laboratory abnormalities resolve to normal or baseline ([Section 7.4.3](#)).

7.4.3. Criteria for Rechallenge of Mavacamten After Potential Hepatotoxicity

The decision to rechallenge the participant should be discussed and unanimously agreed upon by the Investigator and Sponsor.

If signs or symptoms recur with rechallenge, then mavacamten will be permanently discontinued. Participants who clearly meet the criteria for permanent discontinuation (as described in [Section 7.4.1](#)) should never be rechallenged.

7.5. Guidelines for the Management of Exaggerated Pharmacologic Effect (Systolic Dysfunction), Excessive QT Prolongation, or Higher Than Expected Plasma Concentration

If results, as reported by the central laboratories from any visit, show mavacamten plasma concentration is ≥ 1000 ng/mL, or LVEF $< 50\%$ (as read by site), or QTcF meets the following criteria, the participant will be notified by the study site/Investigator for further instructions.

- If QRS is narrow (< 120 milliseconds), then temporary discontinuation criteria are the smaller of: 15% increase from baseline QTcF OR QTcF ≥ 520 milliseconds.
- If QRS is wide (≥ 120 milliseconds), then temporary discontinuation criteria are the smaller of: a 15% increase from baseline QTcF OR QTcF ≥ 550 milliseconds.

It will be communicated to the Investigator and Sponsor that a stopping criterion has been met and the procedures outlined in [Section 4](#) will be implemented. If a participant discontinues study drug permanently, the participant will be encouraged to undergo ET and EOS assessments.

Any participant who experiences heart failure related to systolic dysfunction will be managed as per site-specific standard of care.

7.6. Overdose

An overdose is defined as taking more capsules of study drug than directed. An overdose may be suspected by the Investigator or spontaneously reported by the participant. An overdose may be symptomatic or asymptomatic. Reporting and follow-up of overdose are described below in [Section 7.6.1](#).

In the event of symptomatic overdose or in the presence of significant symptoms and/or clinical compromise, including depressed cardiac contractility or asystole, the Investigator should contact the MyoKardia Medical Monitor, and no further study drug should be administered until further notice.

The participant should be closely monitored clinically for AEs/SAEs, with supportive measures undertaken as clinically indicated. There is no specific antidote for mavacamten. In acute overdose or toxic ingestion, gastrointestinal decontamination should be considered. If necessary, corrective measures, as described in the 2013 ACCF/AHA Guideline for the Management of Heart Failure ([Yancy et al, 2013](#)) and in the 2016 ESC Guidelines for the Diagnosis and Treatment of Acute and Chronic Heart Failure ([Ponikowski et al, 2016](#)) should be implemented. Based on its almost exclusive hepatic metabolism through the CYP 2C19 and CYP 3A4 enzymes, avoidance of inhibitors of these enzymes (eg, omeprazole) is important and administration of inducers of CYP 2C19 and CYP 3A4 may be helpful. The efficacy of other

measures of elimination has not been established. Reintroduction of study drug must be approved by the MyoKardia Medical Monitor.

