--	---

	
Participants who rollover onto commercially available mavacamten at any time will be contacted 8 weeks later by telephone or other technology for an EOS follow-up to assess AEs, concomitant medications, and pregnancy.
 
Telehealth Assessments
 
Telehealth assessments (conducted via telephone or other technology based on standard at institution) will be conducted at Weeks 18, 30, 42, 54, 66, 78, 90, 102, 114, 126, 138, 150, 162, 174, 186, 198, 210, 222, 234, and 246 to assess AEs, concomitant medications, and pregnancy.

Number of Participants	Up to 20 individuals with symptomatic oHCM will be enrolled.
Study Treatment	
Participants will receive mavacamten immediate-release capsules 5, 10, or 15 mg administered QD. The starting dose will be 5 mg for all participants.
 
Each participant has had a Target Dose determined based on his or her PK data from Study MYK-461-004. These doses may only be exceeded for each given participant following discussion between the Investigator and the MyoKardia Medical Monitor. Lower doses are permissible.
 
The Investigator, in conjunction with the Medical Monitor, may also elect to dose reduce a participant after they are on a stable dose of 10 mg or 15 mg treatment for 24 weeks or longer. Participants that have been dose reduced will undergo a follow-up visit 4 to 8 weeks (\pm 7 days) later (to mirror Week 8 assessments, including a TTE assessment). Based on results and clinical symptoms at follow-up visits, subsequent dose decisions will be discussed with the MyoKardia Medical Monitor. This cycle of potential dose reduction and follow-up can be repeated more than once (after at least 24 weeks on a stable dose of 10 mg or 15 mg treatment) and will need to be discussed with the MyoKardia Medical Monitor each time before it is carried out.

Study Duration	The study duration is 264 weeks (up to 4 weeks Screening, 252 weeks treatment [5 years], and 8 weeks posttreatment follow-up) unless the development of mavacamten is stopped or until mavacamten becomes commercially available (at the discretion of MyoKardia). If mavacamten clinical development is discontinued, this study will be terminated. The EOS is defined as the date of the last observation of the last participant.

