7.1. Formulation, Packaging, and Labeling of Study Drug

Mavacamten presentation is size 2, blue opaque capsules printed with a yellow band on the body and black band on the cap. Each capsule contains white to off-white powder. The active capsules are supplied in 3 strengths: 5, 10, and 15 mg.

Mavacamten capsules have been manufactured according to current Good Manufacturing Practice (cGMP) regulations. They will be supplied in high-density polyethylene bottles with induction seals and child-resistant caps at 30 count per bottle. All study drug will be labeled according to applicable local regulatory guidelines.

Mavacamten capsules must be stored at 2°C to 25°C (36°F to 77°F) in the packaging supplied by MyoKardia. Study medication at the investigational site will be stored in a secure area with access limited to authorized study personnel.

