7.3. Treatment Compliance

Compliance with study drug will be monitored by capsule count at each clinic visit ([Table 2](#) and [Table 3](#)).

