10.1.4. Adverse Events of Special Interest

Symptomatic overdose, outcomes of a pregnancy, and LVEF \leq 30% are considered AESIs.

AESIs are required to be reported by the Investigator to the Sponsor within 24 hours, irrespective of regulatory seriousness criteria.

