11.3.8.1. Adverse Events

AEs will be mapped to system organ classes (SOCs) and preferred terms (PTs) using the Medical Dictionary for Regulatory Activities (MedDRA). AEs will be monitored during the study and the data analyzed with respect to overall incidence as well as severity and potential relationship of AEs to study medication. AEs with onset during the treatment-emergent period or with an onset

before the first dose of study medication that increases in severity or becomes serious during the treatment-emergent period, will be considered treatment-emergent.

Adverse event incidence tables will present the number (n) and percentage (%) of participants experiencing at least 1 TEAE by SOC and PT. Multiple occurrences of the same event in the same participant will be counted only once in the tables. The denominator for computation of percentages is the safety population within each treatment group.

AE incidence tables will be provided by treatment group for all types of TEAEs: all TEAEs, all treatment-emergent SAEs, and all TEAEs leading to permanent treatment discontinuation.

Potential Drug-induced Liver Injury

The incidence of liver-related AEs will be summarized by treatment group. The selection of PTs will be based on standardized MedDRA query hepatic disorder.

Deaths

- Deaths will be summarized and listed.

Pregnancy

- Participants who became pregnant during the study will be listed.

Overdose

- Onstudy overdoses will be listed.

11.3.8.2. 12-Lead Electrocardiogram

Twelve-lead ECGs will be obtained in the resting supine position. The RR, PR, QRS, and QT intervals will be measured and read by a central laboratory. Heart rate will be calculated as $60/(RR \times 1000)$ (with RR expressed in milliseconds) and rounded to the nearest integer.

Correction for Heart Rate

Corrected QT interval (QTc) will be calculated using the manually over-read QT values. Each individual ECG QT value will be corrected for HR. The measured QT data will be corrected for HR using QTcF, as per the following formulae/method (with QT, RR, and QTc expressed in milliseconds):

Fridericia's Correction:

$$QTcF = \frac{QT}{(RR / 1000)^{(1/3)}}$$

ECG Numeric Variables

HR, PR, QRS, and QTcF will be summarized using descriptive statistics. The change from baseline of these ECG parameters at each time point will be listed for each participant. For each time point of measurement, the changes from baseline will be summarized using descriptive statistics.

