13.1.2. Study Supplies

MyoKardia will supply or ensure the coordination of sufficient quantities of the following materials to each clinical site:

- Mavacamten active capsules in 3 strengths (5, 10, and 15 mg) in 30-count bottles
- Supplies for laboratory assessments
- Study Reference Manual
- Pharmacy Manual
- IXRS Manual
- IB

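### Overdose is defined by capsule count although three strengths are supplied, so a wrong-strength intake of 1.5 to 3 times the directed dose is outside the overdose report, AESI and listing

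*Combined protocol and SAP*

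**What the plan says.** Section 7.6 gives the only definition: "An overdose is defined as taking more capsules of study drug than directed". Section 7.1 says "The active capsules are supplied in 3 strengths: 5, 10, and 15 mg", and Section 13.1.2 lists the site supplies as "Mavacamten active capsules in 3 strengths (5, 10, and 15 mg) in 30-count bottles". Section 7.1 has a single description of the capsule's appearance, "size 2, blue opaque capsules printed with a yellow band on the body and black band on the cap", which does not distinguish the strengths.

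Directed doses are not fixed. The Synopsis says "The starting dose will be 5 mg for all participants". Section 4 then allows an increase at Week 6 or later, elective reductions from 10 or 15 mg, and restart after a temporary stop one step lower (15 to 10 mg, 10 to 5 mg, with 5 mg unchanged).

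Three provisions use the term overdose:

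- Section 7.6.1 requires a report within 24 hours, with or without symptoms.
- Section 10.1.4 opens its list of AESIs with "Symptomatic overdose, outcomes of a pregnancy".
- Section 11.3.8.1 promises that "Onstudy overdoses will be listed".

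Section 10.1.2 adds that an overdose without side effects is not an adverse event. On compliance, Section 7.3 says "Compliance with study drug will be monitored by capsule count at each clinic visit" and does not mention strength. Section 11.3.5 instead judges each administration against the planned dose.

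**The concern.** The definition counts capsules, while drug exposure depends on milligrams. With one strength the two would agree. With three strengths they can disagree in both directions.

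This matters because the primary objective is long-term safety and tolerability, and Section 8.1 links the most likely risks to higher exposure. An asymptomatic overdose is excluded from the adverse event tables by Section 10.1.2, so the 24-hour report and the listing are its overdose-specific records. If the event does not meet the definition, neither record is created. In a descriptive study of up to 20 participants, one participant is 1/20 = 5% of the Safety Analysis Population at full enrolment, so a single unlisted event is not negligible.

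**Working it through.** The plan gives no figure for this point, so there is nothing to reproduce. The check compares milligrams taken with milligrams directed when the capsule count does not exceed the directed count.

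**Inputs.** Strengths of 5, 10 and 15 mg (Sections 7.1 and 13.1.2); directed daily doses of 5, 10 or 15 mg (Synopsis, Study Treatment); overdose means more capsules than directed (Section 7.6).

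**Same count, higher strength.** Ratio = mg taken / mg directed.

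| Directed | Taken | Ratio | Overdose under 7.6? |
|---|---|---|---|
| one 5 mg | one 10 mg | 10/5 = 2 | No |
| one 5 mg | one 15 mg | 15/5 = 3 | No |
| one 10 mg | one 15 mg | 15/10 = 1.5 | No |

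**Upper bound.** The documents do not say that a dose is always one capsule. Suppose *k* capsules are directed and no more than *k* are taken. The directed amount is at least 5*k* mg and the amount taken is at most 15*k* mg, so the ratio cannot exceed 15*k*/5*k* = 3. The three-fold limit does not depend on one capsule per dose.

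**Opposite error.** Directed one 10 mg capsule, taken two 5 mg capsules: 2 × 5 = 10 mg, ratio 10/10 = 1. This is an overdose under Section 7.6 with no excess drug.

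**Which dose changes create the risk.** Assume that a bottle of the previous strength is kept.

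- After an increase, the old bottle is the weaker one. Taking it by mistake gives 5/10 = 0.5, 5/15 = 0.33 or 10/15 = 0.67 of the directed dose, which is an underdose. Taking the old capsule as well as the new one exceeds the directed count, so the existing definition catches it.
- After a reduction, the old bottle is the stronger one. One restart step gives 15/10 = 1.5 or 10/5 = 2. A ratio of 3 needs a 15 mg capsule held by someone directed to 5 mg: two successive reductions, a direct move from 15 to 5 mg, or a dispensing error.

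**What each provision does with a same-count, wrong-strength intake.**

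| Provision | Depends on the overdose definition? |
|---|---|
| 24-hour overdose report, 7.6.1 | Yes: missed |
| Symptomatic-overdose AESI, 10.1.4 | Yes: missed |
| Overdose listing, 11.3.8.1 | Yes: missed |
| Contact and hold, 7.6 | No: significant symptoms or clinical compromise suffice |
| SAE report within 24 hours, 10.1.3 | No |
| LVEF ≤ 30% AESI, 10.1.4 | No |
| Stopping criteria (≥ 1000 ng/mL, LVEF < 50%, QTcF), 4 and 7.5 | No |
| Noncompliant administration, 11.3.5 | No, but the error must first be recorded |

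**The case against.** The strongest reply is that little is lost beyond a label. A wrong-strength intake with serious consequences is reported as an SAE. Marked symptoms lead to contact with the Medical Monitor and a hold. A high trough, low LVEF or long QTcF leads to the stopping procedure. Section 11.3.5 treats departure from the planned dose as noncompliance. Bottles are labelled (7.1), dispensing records are kept (13.2.2), the interactive response system supports drug distribution (15.1), and a visit is due about 28 days after a dose adjustment (4). Most of this stands, and it limits the point to overdose-specific capture. It does not remove the point: an asymptomatic or non-serious wrong-strength intake need not trigger any of these routes, and Section 7.3 does not require a count that would reveal it.

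A reader might infer more than the documents support:

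- *That contact and hold fails too.* It does not; the instruction in Section 7.6 also applies to significant symptoms without an overdose.
- *That the participants with a Target Dose above 5 mg in Table 1 (11 at 10 mg + 3 at 15 mg = 14 of 20) measure the risk.* They do not. After an increase, the leftover bottle is weaker.
- *That events after such an error would be analysed at the assigned dose.* Section 11.3.8.1 specifies no adverse event analysis by assigned dose level in this single-arm study, and Section 11.3.5 summarises exposure and compliance by treatment actually received.
- *That the capsule's appearance leaves no safeguard.* Section 7.1 describes the capsule; it does not exclude identification by bottle label.

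**Conclusion.** The point holds on the literal text as a misclassification in a reporting definition. A same-count intake of 1.5, 2 or at most 3 times the directed milligrams is not an overdose, and a correct milligram dose taken in more capsules is one. Three overdose-specific provisions are affected; the general safety routes remain.

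The ratios are exact. The frequency is unknown: the documents give no number for dose reductions, retained bottles or dispensing errors, so no expected count can be stated. The leftover-bottle route assumes that superseded bottles stay with participants, which the documents neither say nor rule out. The three-fold case is an extreme, not the typical error. The change is worth making because it costs little and the missed events bear on the exposure-related risk that the protocol itself identifies.

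**What to change.** The sponsor should reconcile the capsule-based definition in Section 7.6 with the three strengths and with the planned-dose wording in Section 11.3.5. For reporting and listing, intake above the currently directed daily milligram amount should be captured whatever the number or strength of capsules. The same meaning should carry through to Sections 7.6.1, 10.1.4 and 11.3.8.1. In Section 7.3, returned capsules should be counted by strength.

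This concerns recording and reporting only. Section 7.6 also uses the term in a drug-hold instruction; how overdose is handled clinically, and whether that instruction needs alignment, is for the sponsor to decide.

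The cost is about one sentence in Section 7.6 and a by-strength line in the accountability record. The downside is that a few more dosing errors will be reported as overdoses, partly offset by dropping those where extra capsules carry no excess drug.

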7.6.1. Reporting and Follow-up of Overdose

If a participant should experience an overdose, the Investigator will report the overdose within 24 hours, even if there are no signs or symptoms associated with the overdose in the participant. Follow-up on the participant's condition will be conducted.

7.7. Prior and Concomitant Treatment

7.7.1. Prior Therapy

At the time of signing the ICF, participants will be asked about their medication history over the previous 30 days, including prescription and nonprescription medications, herbal medications, vitamins, and minerals.

If participants have not taken any prohibited medications in the past 14 days they may proceed to Screening. Participants taking prohibited medications must discontinue treatment for 14 days before proceeding to the Screening assessments.

7.7.2. Concomitant Therapy

Document all concomitant therapies on the appropriate eCRF, whether prescription or over-the-counter, vitamin and/or mineral supplements, herbs, and medications taken for an event or procedure (eg, biopsy). Include start/stop dates, route, and indication.

Background therapy with either beta blockers or calcium channel blockers is permitted if the dose has been stable for 4 weeks at the time of enrollment.

Background cardiomyopathy therapy (eg, beta-blocker, verapamil, or diltiazem) may be adjusted or stopped after a participant has received 24 weeks of mavacamten treatment in this study as determined by the Investigator in conjunction with the MyoKardia Medical Monitor.

The occurrence of concomitant diagnostic/surgical/therapeutic procedures and available details will also be documented on the appropriate eCRF.

7.7.3. Prohibited Therapy

Prior or concomitant treatment with cardiotoxic agents such as doxorubicin or similar is prohibited, as is prior or concomitant treatment with antiarrhythmic drugs with negative inotropic activity (eg, flecainide or propafenone).

The use of disopyramide or ranolazine is prohibited from 14 days before Screening to EOS.

Additional prohibited medications are listed in [Appendix 2](#).

8. RISKS AND PRECAUTIONS

8.1. General

Based on nonclinical data and the available clinical data, the most likely risks are those associated with higher exposures potentially resulting in dizziness or an excessive decrease in LVEF. This could result in the development or worsening of signs or symptoms of systolic heart failure or reduced cardiac output.

Safety testing in other mammalian species has demonstrated that dose-limiting toxicity is related to exaggerated pharmacologic effect and not to off-target adverse effects. For overdose, see [Section 7.6](#).

8.2. Pregnancy

8.2.1. Avoidance of Pregnancy

Females of childbearing potential must use appropriate methods of birth control as listed in [Section 8.2.2](#). Females of nonchildbearing potential are defined as females who are permanently (surgically) sterilized or are postmenopausal. Permanent sterilization includes hysterectomy, bilateral oophorectomy, and bilateral tubal occlusion or ligation at least 6 months prior. Females are considered postmenopausal if they have had amenorrhea for at least 1 year or more following cessation of all exogenous hormonal treatments and follicle-stimulating hormone levels are in the postmenopausal range.

8.2.2. Acceptable Forms of Contraception

Highly effective methods of birth control are defined as those that result in a low failure rate (< 1% per year) when used consistently and correctly. From the time of Screening through 4 months after the last dose of study drug, female participants should practice true abstinence or use effective means of contraception as follows:

- combined (estrogen- and progestogen-containing) hormonal contraception associated with inhibition of ovulation or progestogen-only hormonal contraception associated with inhibition of ovulation by oral, implantable, or injectable route of administration
- IUD
- hormone-releasing IUS
- bilateral tubal occlusion
- Female participant is surgically sterile for 6 months or postmenopausal for 1 year. Permanent sterilization includes hysterectomy, bilateral oophorectomy, bilateral salpingectomy, and/or documented bilateral tubal occlusion at least 6 months prior to Screening. Females are considered postmenopausal if they have had amenorrhea for at least 1 year or more following cessation of all exogenous hormonal treatments and FSH levels are in the postmenopausal range.

Male partners must also use a contraceptive (eg, barrier, condom, or vasectomy).

